11 STUDY COMPLETION AND REMUNERATION

At the last scheduled protocol visit, a study completion form will be completed, which requires the signatures of both the participant and the investigator. The participants will also be provided with a letter of appreciation.

This study involves partial deception which must be explained to the participant at their last study visit (or study exit if discontinued earlier). Each participant will receive an information letter at their last visit which explains the nature of the partial deception and why the study had to be designed in such a way. Each participant will be given time to read, understand and ask questions.

Once their involvement in the study is complete, participants will be informed about receiving feedback following study completion in the Letter of Appreciation.

[REDACTED]

[REDACTED]

12 STATISTICAL ANALYSIS AND DATA MANAGEMENT

12.1 STATISTICAL ANALYSIS

[REDACTED]

[REDACTED] Descriptive statistics will be provided on information regarding baseline variables (age, gender, refractive error distribution, etc.).

Approximately 80 participants will be enrolled and randomized. This is an exploratory study and no formal sample size calculation was performed. The results from this study may be used to determine the appropriate time points and power for future studies.

Analysis of variables will be conducted separately on each eye, and data will not be pooled. The study eye will be defined as the qualified eye with the greatest increase in tear production with stimulation by a cotton swab at the Screening Visit (V1). If both eyes qualify and have the same increase in tear production with stimulation by a cotton swab, then the right eye will be designated as the study eye. Table 4 lists the exploratory outcome variables and anticipated statistical procedures.

Table 4: Statistical procedures

Variable	Analysis	Statistical test
Contact Lens Dry Eye Questionnaire-8 (CLDEQ-8), Comfort (scored immediately after insertion, after 2 hours and immediately before lens removal), Comfortable wear time and Total wear time	Descriptive statistics	Mean, Standard Deviation, Min, Max, Count by visit
	Effect of application by visit (comparison of change from baseline between application groups)	t -test / Wilcoxon rank-sum test (as appropriate)
	Stratified analyses by visit (comparison of change from baseline between application groups stratified by CL freq strata and CL type)	t -test / Wilcoxon rank-sum test (as appropriate)
Pre-lens non-invasive tear breakup time (NITBUT) and Tear meniscus height (TMH)	Descriptive statistics	Mean, Standard Deviation, Min, Max, Count by visit
	Effect of application by visit (comparison of change from baseline between application groups)	t -test / Wilcoxon -rank-sum test (as appropriate)

All data will be tested for normality of distribution using Shapiro-Wilk tests. The appropriate test will be selected based on tests of normality.

The critical alpha level for statistical significance will be set at $p \leq 0.05$, with no adjustments for multiple comparisons. All participants who were evaluated will be used in the analysis. In the event of missing data, individual data points will be excluded in the analysis and not extrapolated from the collected data. As this is a proof of concept, additional statistical analysis may be conducted.

Dependent on the outcome of the study, analysis may be conducted on the contact lenses that have been collected. If the decision is made to not analyse the contact lenses then they will be destroyed according to University guidelines.

Additional analyses may be performed to examine the results observed relative to the device usage recorded by the device itself.

Safety assessments include adverse events, visual acuity and slit lamp biomicroscopy. Summaries by application will be prepared of the number and percentage of subjects reporting one or more adverse events, the number and percentage of subjects reporting one or more device-

related adverse events, the number and percentage of eyes with a clinically significant change in visual acuity at each follow-up exam and the number and percentage of eyes with a clinically significant change in slit lamp biomicroscopy at each visit. A clinically significant change in visual acuity is defined as a change of more than 2 lines (logMAR score change greater than 0.2). A clinically significant change in the slit lamp biomicroscopy parameters will be a change of 2 or more grades.

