4.1 STUDY DESIGN

4.1.1 OVERALL DESIGN

This is a prospective, double-masked, controlled, randomized by device (TrueTear vs TrueTear sham control), parallel arm study, with up to 6 study visits including a screening visit. Study participants (n=80) will be habitual, symptomatic wearers of daily disposable (DD) or reusable hydrogel and silicone hydrogel (SiHy) CLs. Symptomatic participants will be recruited, with a minimum average wear of 2 days/week and ≥ 3 hours of wear/day. It is expected that the majority of symptomatic wearers will be wearing the lenses on average 4-7 days/week. Wearers will be randomized to use the active device or the intranasal sham control.

Visit schedule:

There will be up to 6 study visits and cumulative total time commitment for the study is approximately 6 hours. [REDACTED] Permitted time interval between V1 and V2 is 7- 45 days.

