4.2 STUDY POPULATION

4.2.1 SAMPLE SIZE CALCULATION

Due to the exploratory nature of this study, the planned sample size was determined empirically.

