4.2.2 NUMBER OF PARTICIPANTS

Up to 120 eligible participants will be dispensed / randomized with study products, with a target of 80 completing the study. Informed consent will be obtained for all participants prior to their enrolment in the study.

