10 DISCONTINUATION FROM THE STUDY

Participants discontinued from the study will be reimbursed [REDACTED] for their active involvement in the study (including the initial screening visit). Participants may be discontinued at the discretion of the investigator, sponsor or participant. The following is a list of possible reasons for discontinuation from the study:

- Screening failure: Participants will be discontinued if they do not meet the inclusion and exclusion criteria outlined in section 4.2.3.

- Unacceptable performance with products to be used in study: Participants may be discontinued if they are unable to achieve acceptable comfort and /or vision with the study products, or if they are unable or unwilling to use the intranasal device as instructed.
- Positive slit lamp finding: Participants may be permanently discontinued from the study depending on the severity of the condition and on the judgement of the investigator.
- Adverse event: If a participant experiences an adverse event during the study, they may be discontinued based on the clinical judgement of the investigator or at the participant's request.
- Symptoms: If the participant has persistent symptoms, they may be discontinued based on the clinical judgement of the investigator.
- Disinterest, relocation or illness: The participant may choose to discontinue due to reasons within or beyond their control.
- Violation of protocol or non-compliance: The participant will be discontinued if they are unable or unwilling to follow the protocol specified visit schedules and/or study procedures.
- Instillation of topical ocular medication: The participant will be discontinued if they elect / are required to use a topical ocular medication during the study.
- A confirmed positive pregnancy test at any time during the study.
- Lost to follow-up: The participant will be discontinued if they cannot be contacted and do not return for a final exit visit, and if the investigator has made a reasonable effort to contact the participant for a final study visit.
- Premature termination of the study by the sponsor, the CCLR or the Office of Research Ethics at the University of Waterloo.

A discontinuation form will be completed, which requires the signatures of both the participant and the investigator except where the participant is lost to follow-up in which case only the signature of the investigator is required.

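### The documents use 80 both as the number randomized and as the number completing; separately, a supportive repeated-measures analysis and a by-arm dropout table would be a cheap addition

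*Combined protocol and SAP*

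**What the plan says.** **Sample size.** Three places in the combined protocol and SAP give a number:

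- Section 12.1: "Approximately 80 participants will be enrolled and randomized".
- Section 4.2.2: "Up to 120 eligible participants will be dispensed / randomized with study products, with a target of 80 completing the study".
- Section 4.1.1: "Study participants (n=80) will be habitual, symptomatic wearers", without saying whether these are randomized or completing participants.

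Section 4.2.1 gives the basis: "Due to the exploratory nature of this study, the planned sample size was determined empirically". Section 12.1 likewise says there was no formal calculation.

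**Analysis and missing data.** For the outcomes that Section 2 calls primary (CLDEQ-8, comfort ratings, comfortable wear time, total wear time), Table 4 plans "Effect of application by visit (comparison of change from baseline between application groups", using a t-test or rank-sum test. The missing-data rule is: "In the event of missing data, individual data points will be excluded in the analysis and not extrapolated from the collected data".

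**Discontinuation.** Section 10 includes: "Participants may be discontinued if they are unable to achieve acceptable comfort and /or vision with the study products". The same list allows discontinuation for persistent symptoms.

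**Related provisions.** Table 4 gives counts by visit. Section 14 has status reports counting discontinued and completed participants, with no mention of arm. Section 10 requires a discontinuation form. Section 12.1 adds: "As this is a proof of concept, additional statistical analysis may be conducted". The opening of Section 12.1 is redacted.

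**The concern.** **(a) An inconsistency.** The same figure is the number entering in Section 12.1 and the number finishing in Section 4.2.2. A reader cannot tell how many participants will be analysed, or how precise the estimates are expected to be.

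**(b) A gap that is cheap to close.** Each late-visit test uses only those still giving data, and participants who are doing poorly on comfort or symptoms have a listed route out. If more sham than active participants leave because they are doing poorly, the late-visit device effect is understated. If more active participants do, it is overstated. Section 12.1 says the results may inform time points and power for future studies, so late-visit estimates may be carried forward. The visible text prespecifies neither a dropout sensitivity analysis nor a summary of dropout with reasons by arm.

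**Working it through.** **Plan's own figure.** The 80 cannot be reproduced: it was set empirically, and no effect size, SD or power is given.

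**Step 1: compare the two statements.** With dropout d, 80 completers need N = 80/(1 − d) randomized, and 80 randomized yield 80 × (1 − d) completers.

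| d | Randomized for 80 completers | Completers from 80 randomized |
|---|---|---|
| 0% | 80 | 80 |
| 10% | 89 | 72 |
| 20% | 100 | 64 |
| 33.3% | 120 | about 53 |

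The sections agree only in the first row. The ceiling of 120 allows at most 1 − 80/120 = 33.3% dropout and a gap of at most 120 − 80 = 40 participants.

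**Step 2: precision.** The allocation ratio is not stated in the visible text, so 1:1 is assumed. The 95% half-width for a difference, in SD units, is t(0.975, 2n − 2) × √(2/n).

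- 40 per arm (80 analysed): 0.445.
- 32 per arm (80 randomized, 20% lost): 0.500.
- Ratio: 0.500/0.445 = 1.12, so 12% wider.

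**Step 3: possible bias in the by-visit tests.** All dropout rates and correlations here are assumptions. Suppose participants with the lowest values of a latent score leave, and the score has correlation r with the outcome. With dropout proportion p, the mean among those remaining shifts by r × φ(z_p)/(1 − p). The bias is the difference in shift between arms:

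| Dropout in the two arms | r = 0.3 | r = 0.5 | r = 0.7 |
|---|---|---|---|
| equal | 0 | 0 | 0 |
| 10% vs 15% | 0.02 SD | 0.04 SD | 0.06 SD |
| 10% vs 20% | 0.05 SD | 0.08 SD | 0.11 SD |
| 10% vs 30% | 0.09 SD | 0.15 SD | 0.21 SD |

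The zero in the first row requires dropout to relate to outcome in the same way in both arms. At r = 0.5, the simulated type I error of the nominal 5% t-test for the three unequal rows is 5.5%, 6.5% and 9.4% from 40 per arm, and 5.3%, 6.8% and 11.5% from 60 per arm. Neither size gives exactly 80 completers: at 10% vs 30%, 40 per arm leaves 36 + 28 = 64 and 60 per arm leaves 54 + 42 = 96.

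**Step 4: what a repeated-measures model would recover.** Section 4.5.9 gives eight diary days (3, 6, 8, 12, 15, 18, 21, 24). Simulations at 10% vs 30% dropout show:

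- *Dropout driven by recorded ratings, constant correlation 0.5, compound-symmetry fit:* bias falls from about 0.18 SD to under 0.01 SD. Here the fitted covariance matches the one that generated the data.
- *The same kind of dropout, serially decaying correlation (AR(1), 0.7–0.8), compound-symmetry fit:* a residual of about 0.02–0.04 SD with reversed sign, against 0.08–0.15 SD for available cases. With the correct covariance it is about zero.
- *Latent-score dropout, r = 0.5:* about 0.09 of 0.15 SD remains. At 10% vs 20%, 0.04–0.05 of 0.08 SD remains.

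At 40 per arm, the standard errors of the model and the by-visit test differ by at most 0.242 − 0.234 = 0.008 SD, and the model brings no gain in precision.

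**The case against.** The best defence is that this is an exploratory proof of concept with an empirical sample size and unadjusted tests. The missing-data rule is explicit, Table 4 shows counts, discontinuation forms exist, and further analyses are allowed. This stands in large part. No stated power is invalidated, and the second part is an improvement, not the correction of an error. It does not fully answer the point: permission for extra analyses is not a plan, and visit counts give no reasons for leaving.

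Four stronger readings are tempting, and the documents do not support them:

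- *Section 12.1 is the mistaken sentence.* The unlabelled n=80 in Section 4.1.1 fits either reading, so the documents do not say which section is right.
- *One third attrition is expected, or 40 participants are unaccounted for.* The 120 is a ceiling, so both figures are maxima.
- *The late-visit results will be biased.* No dropout rate is given. At 10% vs 15% and r = 0.5, the bias is 0.04 SD, small beside a half-width of 0.45 SD.
- *A repeated-measures model would all but eliminate the bias.* That holds only when dropout is explained by recorded ratings and the covariance is adequate.

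Because Section 12.1 is partly redacted, it also cannot be claimed that the full plan lacks a dropout summary or supportive analysis.

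**Conclusion.** The point holds, and it is minor.

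(a) The conflict is certain: both sentences are visible, complete and current. What depends on it is expected precision, about 12% in interval width under an assumed 20% loss and 1:1 allocation.

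(b) The mechanism for bias follows from visible rules, but its size rests on assumed inputs. At r = 0.5 it runs from 0.04 SD (10% vs 15%) through 0.08 SD (10% vs 20%) to 0.15 SD (10% vs 30%). The benefit of a supportive model is shown for diary comfort only. Little is gained for CLDEQ-8, which is collected at Visits 1, 4 and 5, and none is shown for comfortable or total wear time.

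**What to change.** **(a)** Reconcile Sections 4.1.1, 4.2.2 and 12.1, and state whether 80 is the number randomized or completing. If Section 4.2.2 is what is intended, Section 12.1 should say that up to 120 will be randomized to obtain about 80 completers, and n=80 in Section 4.1.1 should be labelled as completers. This costs a few words.

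**(b)** Keep the Table 4 tests and the discontinuation rules as they are. Add:

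- One supportive likelihood-based repeated-measures analysis of diary comfort in all randomized participants by assigned arm. Use the end-of-day rating (before lens removal), baseline comfort as a covariate, day-by-arm effects and an unstructured covariance. If that does not converge, use a serially correlated structure, not compound symmetry.
- A table of discontinuation with reasons by arm, from the forms already completed.

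A delta-adjusted sensitivity analysis is optional. It would need a stated range of deltas and an explicit exception to the rule against extrapolating missing data. It would show sensitivity to the assumption without recovering the bias.

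The cost is modest programming and a normality assumption on a bounded 0–100 scale, which is why the Table 4 tests stay. No extra participants, visits or ratings are needed.

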4.1.4 RANDOMIZATION

A randomization schedule will be generated using a web-based program: (www.randomization.com) with stratification by groups based on frequency of lens wear during the week. The final study randomization schedule will be generated [REDACTED] [REDACTED] and provided to the research assistants for the study. Study investigators will remain masked to the randomization schedule until the study is completed and the database is locked.

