4.5.9 COMFORT RATINGS

Participants will be asked to complete subjective ratings at the study visits and at home on certain study days. They will record their responses on an online database [REDACTED]

[REDACTED] Responses will be captured at screening, on study day 0 (at V2-1, V2-2), and subsequently at days 3, 6, 8, 12, 15, 18, 21, and 24 where comfort will be recorded after lens insertion, after 2 hours of lens wear and prior to lens removal at the end of the wearing day. Comfort will be assessed on a 100 point scale with a score of 0 indicating "Extremely uncomfortable" and a score of 100 indicating "Extremely comfortable." Verbal instructions on how to complete the diary will be provided and email reminders will be sent to the participant for each rating. The CLDEQ-8 questionnaires will also be completed at Visit 1, 4 and 5 using the [REDACTED] on the participant's phone. The individual assessments on the CLDEQ-8 questionnaire will be summarized to provide a score of 1 to 37.

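### Table 4 compares unadjusted change scores between arms; one prespecified model with baseline and wear-frequency stratum would be more precise at no cost

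*Combined protocol and SAP*

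**What the plan says.** Table 4 in section 12.1 covers CLDEQ-8, comfort, comfortable wear time and total wear time, and in a second block NITBUT and TMH. For all of them the overall arm comparison is "Effect of application by visit (comparison of change from baseline between application groups". The test is a t-test or "Wilcoxon rank-sum test (as appropriate". The choice between them is data-driven: "The appropriate test will be selected based on tests of normality", with Shapiro-Wilk named.

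Section 4.1.4 randomizes "with stratification by groups based on frequency of lens wear during the week". In Table 4 the strata appear only in a separate row for the first group of outcomes: "Stratified analyses by visit (comparison of change from baseline between application groups stratified by CL freq strata and CL type". That row lists the same two-sample tests. It names no combined stratum-adjusted estimate and no interaction test.

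Section 4.5.9 collects comfort at screening, on day 0 and "subsequently at days 3, 6, 8, 12, 15, 18, 21, and 24 where comfort will be recorded after lens insertion". Section 12.1 gives one use for the results: "The results from this study may be used to determine the appropriate time points and power for future studies".

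**The concern.** Subtracting baseline fixes the slope of follow-up on baseline at 1. If the true slope is lower, as is usual when a measure regresses to its mean, the change score over-corrects and carries avoidable noise. The overall comparison also ignores the factor that the randomization balances.

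No stated power claim is at risk, because the plan makes none. At stake is the use the plan gives for its results. Planning power needs a precise effect and the residual SD of the model a later trial would use. Choosing time points needs one effect measure on the same scale at every day. The plan does not say whether the normality check is made once per outcome or again at each day. If it is made per day, comfort could be compared by means on some days and by ranks on others. Separate p-values within strata do not show whether the effect differs by wear frequency or lens type.

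**Working it through.** The plan gives no effect size, SD, power or correlation, so there is no figure of its own to reproduce.

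**Inputs from the plan.** About 80 participants (section 12.1; section 4.2.2 has up to 120 randomized and 80 completing). Alpha 0.05, "with no adjustments for multiple comparisons" (section 12.1).

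**Assumptions.** 1:1 allocation, so 40 per arm; two-sided tests; correlation rho between baseline and follow-up of 0.3 to 0.8; equal SDs at both times. The unit is the SD of a single measurement, and the effect for power is 0.5 SD.

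**1. Direction.** Per participant, the change-score variance is SD_base² + SD_post² − 2·rho·SD_base·SD_post. The ANCOVA residual variance is SD_post²(1 − rho²). The difference is (SD_base − rho·SD_post)², which is never negative and is zero only when the slope of follow-up on baseline is 1. Estimating the slope costs a factor of about 1 + 1/76, roughly 1% of variance at N = 80.

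**2. Size.** With equal SDs the variances are 2(1 − rho) and 1 − rho², so their ratio is (1 + rho)/2. The SE is √(variance × 2/40), and the 95% CI half-width is 1.991 × SE. At rho = 0.5 the change score gives 1.991 × √(1.00 × 0.05) = 0.445, and ANCOVA gives 1.991 × √(0.75 × 0.05) = 0.386. Equivalent N is 80 divided by the ratio. Power uses the noncentral t distribution. The table leaves out the 1% covariate cost.

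| rho | Variance: change / ANCOVA | Ratio | Equivalent N | CI half-width (SD) | Power for 0.5 SD |
|---|---|---|---|---|---|
| 0.3 | 1.40 / 0.91 | 0.65 | 123 | 0.53 to 0.42 | 46% to 64% |
| 0.5 | 1.00 / 0.75 | 0.75 | 107 | 0.45 to 0.39 | 60% to 72% |
| 0.7 | 0.60 / 0.51 | 0.85 | 94 | 0.34 to 0.32 | 81% to 87% |
| 0.8 | 0.40 / 0.36 | 0.90 | 89 | 0.28 to 0.27 | 94% to 96% |

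At rho = 0.9 the variance gain is only 5%.

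**3. The same gain within a single trial.** The difference in baseline means has SE √(2/40) = 0.224 SD. A chance imbalance of 0.2 SD or more therefore occurs in 37% of trials (|Z| ≥ 0.2/0.224). An imbalance of exactly 0.2 SD moves the change-score estimate by (1 − rho) × 0.2, which is 0.14, 0.10, 0.06 and 0.04 SD at the four correlations. ANCOVA removes this shift. It is not an extra gain, since 2(1 − rho) − (1 − rho²) = (1 − rho)².

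**4. Strata.** Simulation of 20,000 trials with two strata of 40 and arms balanced within strata (the number of strata is an assumption). If the strata explain 10%, 20% or 30% of the variance in change, the unadjusted t-test has a type I error of about 4%, 3% or 2%, so it is conservative. If they explain the same shares of stable levels only, they cancel in the change and the error stays at about 5%.

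**5. Stratified row.** Within one of two equal strata (20 per arm), power for 0.5 SD on the change score is 26%, 34%, 51% and 68% at the four correlations.

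**6. Choice of test.** Suppose normality is tested afresh on each of the 8 diary days and the data are exactly normal. With independent days, at least one day switches to Wilcoxon with probability 1 − 0.95⁸ = 34% if the arms are pooled for the check, or 1 − 0.95¹⁶ = 56% if each arm is checked. Simulation with correlated days (500 trials per setting) gave a mixture of tests in 30% to 32% and 54% to 55% of trials. Across all simulated settings, including bounded skewed scores, the ranges were 30% to 53% and 49% to 69%.

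**The case against.** The strongest reply is that no stated aim fails. The study is exploratory, the planned comparison is unbiased, and section 12.1 leaves room for further analyses. Table 4 already reports means and SDs by visit, and under section 12.2 the sponsor can obtain the data and fit any model later. This stands as far as validity goes. It does not remove the case for the change: a model chosen after the data are seen lacks the protection of prespecification, and naming it now costs nothing.

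Several narrower points also stand:

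- Variance, equivalent N, interval width, power and baseline imbalance all express one gain. It rests on an assumed rho and is small at 0.8 and above.
- Nothing in the documents suggests that wear frequency predicts change. If it predicts only levels, omitting it does no harm to the planned test. Section 4.1.4 also states no block structure in its readable text.
- Choosing the test by Shapiro-Wilk does little to error rates. In simulations of a single comparison it moved type I error by at most about 0.2 percentage points and power by about 0.5. The objection to it is the changing effect scale, and only if selection is per day.
- The plan does not claim that within-stratum p-values show effect modification. Table 4 nevertheless offers no other means of comparing the strata.

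Two limits come from the documents. The opening of section 12.1 is redacted, so this point concerns Table 4, the plan's own list of procedures. The readable text also does not say whether baseline is screening or a day 0 rating. That does not favour the planned analysis, because a change score needs the same definition.

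**Conclusion.** The point holds as a matter of efficiency, not of validity. Table 4's overall comparison is unbiased over repeated randomizations and does not inflate false positives, but it uses the baseline inefficiently and ignores the randomization stratum. That adjustment is at least as precise is certain apart from the roughly 1% covariate cost. The amount is not certain: 10% to 35% of variance for rho between 0.8 and 0.3 with equal SDs, or 80 participants doing the work of 89 to 123. Any further gain from the stratum depends on wear frequency predicting change. The figures on mixed tests are conditional on per-day selection and do not carry the conclusion. The change should be made, because the results are meant to help plan later studies and nothing has to be given up for it.

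**What to change.** In Table 4, make the main comparison a linear model of the follow-up value on arm, the baseline value already used for the change score, and the wear-frequency randomization stratum. State for each outcome which assessment is the baseline. Report the adjusted mean difference with its 95% CI, and the residual SD, for the four primary outcomes, NITBUT and TMH. Use this one method at every visit and diary day.

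Replace selection by Shapiro-Wilk with a rank-based sensitivity analysis, for example a van Elteren test stratified by wear frequency. Keep the results by wear frequency and lens type as descriptive subgroup estimates, and use arm-by-subgroup interaction terms in place of within-stratum tests.

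The cost is SAP wording only. Table 4's change scores already require the baseline values, and the randomization already requires the stratum. No participants, visits or measurements are added.

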2 OBJECTIVES

The objective of this study is to evaluate the increase in comfort and comfortable CL wear time associated with application of TrueTear (active intranasal neurostimulation) compared with application of TrueTear sham control (intranasal application which is not electrically active) in symptomatic CL wearers.

The primary outcome variables for this study are:

- Contact Lens Dry Eye Questionnaire (CLDEQ-8)
- comfort ratings
- comfortable wear time (CWT)
- total wear time (total WT)

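### No procedure in Table 4 combines a participant's repeated comfort ratings; a baseline-adjusted repeated-measures model would gain precision, by an amount the documents do not fix

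*Combined protocol and SAP*

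**What the plan says.** - Section 2 introduces a list of four outcomes with "The primary outcome variables for this study are"; comfort ratings are one of them. Section 3 makes comfort part of the hypothesis.
- Section 4.5.9 says participants will "complete subjective ratings at the study visits and at home on certain study days". After screening and day 0, ratings follow "subsequently at days 3, 6, 8, 12, 15, 18, 21, and 24", and on these days "comfort will be recorded after lens insertion, after 2 hours of lens wear and prior to lens removal".
- Section 12.1, Table 4, lists the three comfort ratings with CLDEQ-8 and the two wear times. The between-arm analysis is "Effect of application by visit (comparison of change from baseline between application groups", with the test given as a t-test or "Wilcoxon rank-sum test (as appropriate". A second row repeats it within wear-frequency and lens-type strata. Descriptive statistics are also by visit.
- Section 12.1 gives the study's use: "The results from this study may be used to determine the appropriate time points and power for future studies". It states no effect size, SD or power. It also drops missing data points and permits further analyses without naming a method.

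**The concern.** Eight days at three moments is 24 scheduled ratings per participant after dispensing. Sections 4.1.1 and 4.4 allow six visits including screening, and section 4.5.9 places V2-1 and V2-2 on day 0. That leaves three later visits (6 − 1 − 2), so at most three of the eight rated days can coincide with a visit. The visible text does not say how the other days enter a by-visit comparison: left out, tested singly, or averaged within an interval.

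Two things are at stake. A single-day rating carries day-to-day noise that combining days would reduce without recruiting anyone. And if each day is tested alone, a constant effect can look as if it comes and goes, which matters in a study meant to inform the time points of later ones.

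**Working it through.** **Plan's own figure.** There is none to reproduce. The size of about 80 was set empirically, with no effect size, SD or power.

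**Inputs.** From the documents: 8 rated days, 3 moments (kept separate because they measure different things), about 80 participants, alpha 0.05. Assumed: 1:1 allocation (40 per arm), a two-sided test, an effect constant over days of 0.5 SD of the single-day change score, complete data, and the correlations below.

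**Formulas**, in units of the variance of one day's rating, with rb the baseline-to-day and rp the day-to-day correlation:
- single-day change: 2(1 − rb)
- change of the 8-day mean: (1 + 7rp)/8 + 1 − 2rb
- 8-day mean adjusted for baseline: (1 + 7rp)/8 − rb²
- correlation between two days' change scores: c = (1 + rp − 2rb) / [2(1 − rb)]
- variance of a k-day mean change relative to one day: (1 + (k − 1)c)/k

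If rb = rp, then c = 0.5 whatever their common value. If rated days correlate more with each other than with baseline, c exceeds 0.5.

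**Averaging only.** Power is from the noncentral t with 78 df and noncentrality 0.5·√20/√ratio. For one day this is 2.236, giving 60%.

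| c | Variance ratio, 8 days | Effective sample size | Power, 8 days | Power, 5 days |
|---|---|---|---|---|
| 0.5 | (1 + 3.5)/8 = 0.5625 | 1.78-fold | 84% | 81% |
| 0.7 | (1 + 4.9)/8 = 0.7375 | 1.36-fold | 73% | 72% |
| 0.8 | (1 + 5.6)/8 = 0.825 | 1.21-fold | 68% | 67% |
| 0.9 | (1 + 6.3)/8 = 0.9125 | 1.10-fold | 64% | 63% |

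The 5-day column matters because section 4.2.3 admits people who wear lenses 2 days a week. Days 3 to 24 span 22 days, so such a person has about 2 × 22/7 ≈ 6 wearing days and may supply fewer than 8.

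**Averaging plus baseline as covariate.** At rb = 0.5 the single-day change has variance 1 and c = rp. With rp = 0.9 the adjusted variance is 0.9125 − 0.25 = 0.6625, giving 77% power against 64% without adjustment. With rp = 0.7 it is 0.7375 − 0.25 = 0.4875, giving 89% against 73%.

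**Why baseline must be in the model.** Take rb = 0.7 and rp = 0.8. The 8-day mean of raw ratings, unadjusted, has variance (1 + 5.6)/8 = 0.825. The planned single-day change score has 2 × 0.3 = 0.60. Pooling days without baseline can therefore be less precise than the planned test.

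**Eight separate tests.** Simulating 20,000 trials per setting with the constant 0.5 SD effect, some but not all of the eight tests were significant in about 76% of trials at c = 0.5, 60% at 0.7, 49% at 0.8 and 35% at 0.9.

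**The case against.** The strongest case against has four parts.

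- **The size of the gain is not known.** A reader might infer that much precision is certainly lost. The documents give no SD or correlation. The 1.78-fold figure needs baseline to correlate with each rated day as strongly as those days do with one another. That is doubtful: rated days are 2 to 4 days apart and all follow dispensing, and if the screening rating is the baseline it may lie 7 to 45 days before V2. At c = 0.9 averaging alone gains little.
- **The study is exploratory.** It has no power target, and looking at each time point fits its aim of choosing time points. This stands as a reason to keep the day-by-day display. It does not favour reading isolated p-values as that display.
- **A time course is still available.** A reader might infer that single-day tests cannot show one. They can: Table 4 gives summaries and arm comparisons by visit, and if days are handled the same way those estimates form a time course. The weakness lies in judging it by significance.
- **Text is redacted.** Parts of 12.1, the visit schedule and 4.5.9 are blacked out, so averaging within a visit interval cannot be excluded. Nor do the documents support treating all eight days as home days. Table 4 itself is legible, however, and names no method that combines days. The general permission for further analyses does not fill that gap.

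**Conclusion.** The point holds in a bounded form. The visible plan schedules up to 24 post-dispensing comfort ratings per participant and states no procedure that combines them across days. Under the stated assumptions, averaging eight days lifts power from 60% to between 64% and 84%, depending on a correlation the documents do not give; baseline adjustment raises it further. These figures are for a constant effect and a full set of rated days, so eight days is a ceiling for infrequent wearers. The planned tests remain valid without the change; what is lost is information already being collected, and a sound basis for choosing time points. It should be changed before analysis.

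**What to change.** In Table 4, add as the main comfort comparison one repeated-measures mixed model per rating moment, using all rated post-dispensing days:

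- The outcome is the rating, with baseline comfort as a covariate. State which rating is the baseline.
- Terms are arm, day, arm-by-day and wear-frequency stratum, with within-participant correlation.
- Report the arm difference averaged over a set of days fixed in advance, with a 95% CI.
- Name one rating moment as the lead.
- Keep the by-visit and by-day estimates, with CIs, alongside as the time course.
- State how rated days that are not visits enter the table.
- Report the estimated within-participant correlation, which planning a later repeated-ratings study needs.

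Apply the same model to comfortable and total wear time only if these are recorded on several days; the visible text does not say.

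The cost is SAP wording and a little more analysis work. The model uses every observed rating, so the rule against filling in missing points can stay. The drawback is that an average dilutes an effect that appears only late; the day-by-day display would show it.
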